		Baseline (Dose 1)			Week 2 (Dose 2)			Week 4 (Dose 3)			Week 8, 12, 16, 20, and 24	Week 28 OR (4 Weeks After Last Dose)	Week 32 OR (8 Weeks After Last Dose)		
Tests and Assessments 	Day -28 to Day -1	Day 1 (±3 days)			Day 15 (±3 days)			Day 29 (±3 days)			Days 57, 85, 113, 141, and 169 (±3 days)			Day 197 OR 4 Weeks After Last Dose (±3 days)	Day 225 OR 8 Weeks After Last Dose (±3 days)
		Pre dose	LP	Post dose	Pre dose	LP	Post dose	Pre dose	LP	Post dose	Pre dose	LP	Post dose		
Study Drug Administration 			X			X			X			X			
AE and Concomitant Therapy and Procedures Recording		-----X (ongoing)-----													
SAE Recording		-----X (ongoing)-----													

[figure not shown]
 Some sites may only participate in screening procedures.

 After completing the EOS Visit, participants will be considered study completers and will have the option to participate in the LTE study 233AS102 (see Section 7.5).

 Participants who terminate early (i.e., discontinue both study treatment and assessments) will be asked to complete the assessments of the EOS Visit within 4 weeks after the last dose of study treatment (see Section 10.1).

[figure not shown]
 Participants who do not roll over into the LTE study will have an additional safety FU visit at Week 32 or 8 weeks after the last dose of study treatment. For participants with delays between their Week 28 Visit and enrollment in the LTE study, a Safety FU (Alternative EOS) Visit will be conducted (either in person or by telephone contact) to collect AEs, SAEs, and concomitant medications or procedures. This Safety FU (Alternative EOS) Visit can be performed at Week 32 or prior to (within 2 days) enrollment in the LTE, whichever comes first.

 All visits are expected to take place on site unless participants are unable to travel to the site; then, a home visit may be possible at the discretion of the Investigator.

CONFIDENTIAL

The information contained herein may not be used, disclosed, or published without the written consent of Biogen MA Inc.

-  Telephone contact to be performed approximately 24 hours after LP.
-  Predose assessments can be performed in a single visit up to 2 days prior to dosing.

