### **7.3.3.3. Part C: Pivotal**

Participants participating in Part C (Pivotal) will return to the site for an EOS Visit 4 weeks after their last dose (at Week 28), as described in the Schedule of Activities ([Table 3](#)) they will have the option to participate in the LTE study (233AS102), if eligible. This will be done without unblinding the treatment group.

For participants with delays between their Week 28 Visit and enrollment in the LTE study, a Safety FU (Alternative EOS) Visit will be conducted (either in person or by telephone contact) to collect AEs, SAEs, and concomitant medications or procedures. This Safety FU (Alternative EOS) Visit can be performed at Week 32 or prior to (within 2 days) enrollment in the LTE, whichever comes first.

Participants who do not roll over into the LTE study will have an additional safety FU visit 8 weeks after their last dose (at Week 32) to collect information on AEs, SAEs, and concomitant medications or procedures (in person or by telephone contact).

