#### **7.5. End of Study**

The EOS is last participant, last visit for Part C (either in person or by telephone contact). In the event of a decision by the Sponsor to terminate the study earlier on the grounds that conducting a placebo-controlled study is no longer deemed ethical based on the assessment of risk-benefit of Study 233AS101, all participants will be invited for the EOS Visit, during which all Week 28 assessments will be conducted. The EOS Visit should occur 4 weeks after the last dose of study

CONFIDENTIAL

The information contained herein may not be used, disclosed, or published without the written consent of  
Biogen MA Inc.

treatment. After completing the EOS Visit, participants will be considered study completers and they will have an option to participate in the LTE study, if eligible. For participants with delays between their Week 28 Visit and enrollment in the LTE study, a Safety FU (Alternative EOS) Visit will be conducted (either in person or by telephone contact) to collect AEs, SAEs, and concomitant medications or procedures. This Safety FU (Alternative EOS) Visit can be performed at Week 32 or prior to (within 2 days) enrollment in the LTE, whichever comes first. For participants not entering the LTE study or in the event the study is stopped early, there will be an additional safety FU visit 8 weeks after the last dose of study treatment.

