## **10. DISCONTINUATION OF STUDY TREATMENT OR WITHDRAWAL OF PARTICIPANTS FROM THE STUDY**

### **10.1. Withdrawal from the Study (Part A) or Discontinuation of Study Treatment (Parts B and C)**

A participant *must* be withdrawn from Part A of the study (SAD), or permanently discontinue study treatment in Part B (MAD) and Part C (Pivotal) of the study, for any of the following reasons:

- The participant becomes pregnant. Study treatment must be discontinued immediately. Report the pregnancy according to the instructions in Section [15.4.1](#).
- The participant withdraws consent to continue study treatment.
- The participant experiences a medical emergency that necessitates permanent discontinuation of study treatment.
- The participant experiences a medical emergency that necessitates unblinding of the participant's treatment assignment.
- The participant is unwilling or unable to comply with the protocol.
- At the discretion of the Investigator or Sponsor.

The reason for discontinuation of study treatment must be recorded in the participant's CRF.

Participants who discontinue treatment in Part B may remain in the study and continue protocol-required tests and assessments.

Participants who discontinue study treatment in Part C will be encouraged to remain in the study and complete all appropriate protocol-specified tests and assessments. It is recommended that participants who terminate early (i.e., discontinue both study treatment and study assessments) perform the assessments of the EOS Visit (Week 28 Visit) within 4 weeks after the last dose of study treatment. Home assessments will be allowed at the discretion of the Investigator for participants who cannot come to the site in person for their Early Termination Visit.

CONFIDENTIAL

The information contained herein may not be used, disclosed, or published without the written consent of Biogen MA Inc.

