## **11.3. Concomitant Therapy and Procedures**

### **11.3.1. Concomitant Therapy**

A concomitant therapy is any drug or substance administered between Day 1 and the final study visit (Day 57 for participants participating in Part A [SAD] only; Day 169 for participants participating in both Parts A [SAD] and B [MAD] or in Part B [MAD]; and Day 197 or Day 225 for participants participating in Part C [Pivotal] only).

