#### 15.3.2. Serious Adverse Events

Any SAE experienced by the participant between the time of the signing of the first (main) ICF and the last FU visit is to be recorded on an SAE form, regardless of the severity of the event or its relationship to study treatment. SAEs must be reported to Biogen within 24 hours as described in Section 15.3.3. FU information regarding an SAE also must be reported within 24 hours.

Participants will be followed for all SAEs until the final study visit. Thereafter, the event should be reported to Biogen only if the Investigator considers the SAE to be related to study treatment.

Any SAE that is ongoing when the participant completes or discontinues the study will be followed by the Investigator until the event has resolved, stabilized, or returned to baseline status.

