### Reporting Information for SAEs

A report ***must be submitted*** to Biogen regardless of the following:

- Whether or not the participant has undergone study-related procedures
- Whether or not the participant has received study treatment
- The severity of the event
- The relationship of the event to study treatment

To report initial or FU information on an SAE, fax or email a completed SAE form; refer to the Study Reference Guide for complete contact information.

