- Summary statistics: difference between treatment groups in least square means of Day 197 change from baseline with corresponding standard errors and 95% confidence intervals taken from the ANCOVA for change from baseline to Day 197, based on the MI datasets. The ANCOVA model will include treatment group as a fixed effect and covariates for ALSFRS-R total score, baseline disease duration since symptom onset, and use of riluzole or edaravone.

For the JRT analysis, the ranked scores will be analyzed for each of the 100 MI-complete datasets using an ANCOVA model with treatment included as a fixed effect and adjusted for the following covariates: baseline disease duration since symptom onset, baseline ALSFRS-R total score, and use of riluzole or edaravone. The p-value will be based on combining the estimates for the treatment differences using PROC MIANALYZE. The difference between treatment groups in median changes from baseline to each visit will be presented with 95% confidence intervals based on the MI datasets, as well as the p-value from the JRT for Day 197. The joint rank analysis will only be performed for the mITT population.

The joint rank procedure allows for a statistical test of the treatment effect on the ALSFRS-R total score while accounting for truncation of data due to deaths. In this analysis, a participant's joint rank score will be calculated by comparing each participant to every other participant in the

CONFIDENTIAL

The information contained herein may not be used, disclosed, or published without the written consent of  
Biogen MA Inc.

study, resulting in a score of +1 if the outcome was better than the participant being compared, -1 if worse, and 0 if the same. The participant's score will then be calculated by summing their comparison to all the other participants in the study.

For the purpose of this calculation, participants will be grouped into the following 2 categories:

- Group 1: Participants who complete the study and have data available at the Day 197 assessment AND participants who withdraw from the study due to reasons other than death
- Group 2: Participants who die

MI will be used to impute all missing data before determining the rank score, including intermittent data and data after withdrawal from the study except after death.

In each of the 100 imputed datasets, participants will be ranked as follows:

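### Part C requires no vital-status check to Day 197 after full withdrawal, although death is ranked worst and a death count selects the primary test; the expected effect is small and the fix is cheap

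*Protocol*

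**What the plan says.** **Analysis.** Section 16.2.1.2.1 sets two scenarios for the mITT population. With 3 or more deaths across both arms, the joint rank test carries the primary inference; with fewer, ANCOVA with multiple imputation does. The p-value of the method not chosen is reported as a sensitivity analysis. Group 2 is participants who die, ranked below all of Group 1. Group 1 is completers with Day 197 data plus "participants who withdraw from the study due to reasons other than death", whose missing values are imputed except after death. Section 16.2.1.2.2 adds time to death or permanent ventilation and time to death as secondary endpoints.

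**Data collection after leaving.** Section 10.1 encourages those who stop treatment to stay in the study. For those who stop everything it says: "It is recommended that participants who terminate early (i.e., discontinue both study treatment and study assessments) perform the assessments of the EOS Visit", within 4 weeks of the last dose. Table 3, footnote 4 says that participants who do not roll over into the extension study "will have an additional safety FU visit at Week 32 or 8 weeks after the last dose of study treatment"; Sections 7.3.3.3 and 7.5 have the same 8-week contact.

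**Reporting.** Section 15.3.2 follows all SAEs to the final study visit and then narrows: "Thereafter, the event should be reported to Biogen only if the Investigator considers the SAE to be related to study treatment". Section 15.3.3 requires SAE reports whatever the relationship to treatment, and Section 15.3.3.1 requires all causes of death to be reported within 24 hours of the site becoming aware.

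**The concern.** The ranking, the choice of primary test and both time-to-event endpoints assume that deaths up to Day 197 are known. For a participant who has withdrawn completely, the protocol has no step that finds out. The last contact is tied to the last dose, and the death-reporting duty starts only when the site happens to learn of the event.

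A death in the uncovered period has three consequences. The participant stays in Group 1 with an imputed function score instead of a place at the bottom. The death is missing from the count that chooses between the joint rank test and ANCOVA. The participant is censored in both time-to-event analyses. The composite strategy then gives a good or average outcome to someone who had the worst one. The SAP is not shown, but no SAP could repair this, because it can define who is in Group 2 but cannot supply a status that was never collected.

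**Working it through.** **1. The plan's own power.** Inputs from Section 16.2.7: N = 60, means −0.74 and −3.83, SD 3.166, Week 28 survival 90% (active) and 82% (placebo), two-sided 0.05, stated power 84%. The 2:1 allocation gives 40:20. Simulating the joint rank test (exponential death times, deaths ranked lowest by time, t-test on ranks, no covariates, 40,000 runs) gives 85.6%, so the stated figure reproduces to within 2 points.

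**2. Days not covered before Day 197.** Gap = max(0, 197 − (last dose day + 56)) if the 8-week contact happens, or with + 28 if only the 4-week visit does.

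| Last dose (day) | 1 | 15 | 29 | 57 | 85 | 113 | 141 | 169 |
|---|---|---|---|---|---|---|---|---|
| 8-week contact | 140 | 126 | 112 | 84 | 56 | 28 | 0 | 0 |
| 4-week visit only | 168 | 154 | 140 | 112 | 84 | 56 | 28 | 0 |

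**3. Risk of death in a gap.** Constant daily hazards are −ln(0.90)/197 and −ln(0.82)/197, and risk = 1 − exp(−hazard × gap).
- 56 days: 2.95% active, 5.49% placebo; average (40 × 0.0295 + 20 × 0.0549)/60 = 3.8%, or about 26 full withdrawals per missed death.
- 140 days: 7.21% and 13.15%; average 9.2%, or about 11 full withdrawals per missed death.

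**4. Missed deaths and the 3-death rule.** Expected deaths = 40 × 0.10 + 20 × 0.18 = 7.6. The protocol gives no withdrawal rate, so 5% to 20% is assumed, with no site learning of the deaths. Missed deaths = w × (40 × active risk + 20 × placebo risk).
- w = 5%, 56 days: 0.05 × (40 × 0.0295 + 20 × 0.0549) = 0.11.
- w = 20%, 140 days: 0.20 × (40 × 0.0721 + 20 × 0.1315) = 1.10.

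The chance of counting fewer than 3, from the sum of Bin(40, 0.10 − w × active risk) and Bin(20, 0.18 − w × placebo risk):

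| Withdrawal, gap | P(fewer than 3 counted) |
|---|---|
| none | 1.34% |
| 5%, 56 days | 1.49% |
| 10%, 56 days | 1.64% |
| 10%, 140 days | 2.18% |
| 20%, 140 days | 3.48% |

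**5. Power and error of the joint rank test.** Deaths in the last 140 days of withdrawn participants are treated as unrecorded and replaced by a draw from the arm's survivor distribution.
- Power with 0%, 10% or 20% withdrawal in both arms: 85.6%, 86.4%, 86.8%.
- No true effect (mortality 7.6/60 = 12.67% in both arms), rejection in favour of active: 2.4% with no loss; 2.5% with 20% in both arms; 3.2% with 20% active and 5% placebo; 2.1% with those reversed. Repeat runs of the 20%/5% case gave 2.9% to 3.0%.

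**6. If mortality is lower.** With assumed survival of 96% and 92%, expected deaths are 40 × 0.04 + 20 × 0.08 = 3.2, close to the threshold. In a simulation where every death after withdrawal goes unseen, the primary test switches in 3.6% of trials at 10% withdrawal and 7.4% at 20%, with power changing by less than 1 point.

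**The case against.** The strongest reply is that nothing is misstated. Withdrawal is itself a named intercurrent event, ranked on its imputed value, so someone who leaves for another reason and later dies can be read as belonging in Group 1. Section 16.2.1.2.1 leaves further details to the SAP. That reading is possible, but Group 2 is simply those who die, and imputation is barred after death. Which group applies is a definition the SAP could settle; whether the death is known is not.

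The protocol also does more than nothing. Table 3, footnote 3 says early terminators will be asked to complete the EOS assessments, and home assessments are allowed. SAEs open at discontinuation are followed until resolved or stable, and Section 15.6.1 tells investigators to pursue SAE follow-up persistently. Section 11.3.1 gives the final visit as "Day 197 or Day 225 for participants participating in Part C [Pivotal] only", so SAE follow-up could be read as running to Day 197. These points narrow the gap. They do not close it: Section 11.3.1 concerns concomitant therapy and schedules no contact, and the other duties start from an event the site already knows about. The consent text and the adjudication charter (Section 19.3.3) are not shown, and a vital-status clause in either would answer the point.

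The objection on size largely stands. The 3.2% is one tail of a two-sided test. A rerun of that case gave 3.0% for active and 2.2% for placebo, 5.2% in total. It also needs a 140-day gap for every withdrawal. With last doses spread evenly over the eight visits and the 8-week contact made (mean gap 546/8 = 68 days), the same 20%/5% split gives 2.7% for active, 5.0% in total and 0.4 missed deaths.

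**Conclusion.** The concern holds as a minor one. The protocol has an analysis that depends on knowing deaths to Day 197, and no step that establishes them after full withdrawal.

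At the planned mortality, and assuming 5% to 20% full withdrawal with 56- to 140-day gaps, about 0.1 to 1.1 deaths would be missed, and the chance of falling below the 3-death threshold stays at 3.5% or less. Equal loss does not reduce power. Unequal loss shifts error between the two tails by under 1 percentage point, and the two-sided rate stays near 5%. If the test did switch, the joint rank p-value would still be reported as a sensitivity analysis.

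The result rests on constant hazards, the same mortality after withdrawal as before it, a simple imputation without covariates, and no site hearing of the deaths by other means. It is less secure if mortality is well below plan, if withdrawal differs by arm, or if those who leave die sooner.

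**What to change.** In Sections 10.1 and 15.3, require vital status and date of death through Day 197 for every dosed Part C participant, including those who withdraw, by telephone, medical record or public record as consent allows. In Section 16.2.1.2.1, state that deaths on or before Day 197, whether or not the participant had already withdrawn, define Group 2 and enter the count of 3.

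The cost is a short amendment, a consent line if none exists, and one status check per full withdrawal. Sample size does not change. Status may remain unobtainable where consent is withdrawn entirely; those cases should be counted and reported by arm.

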### 16.2.1.2.2. Analysis of the Secondary Efficacy Endpoints

Formal testing of secondary efficacy endpoints will be in the mITT population alone. For the non-mITT and ITT populations, there will be no formal testing of efficacy endpoints. Testing of PD endpoints is discussed in Section 16.2.3. The analyses of secondary endpoints for the mITT population will be based on a sequential testing procedure in the order of the rank of secondary endpoints as listed below if the primary endpoint is statistically significant at a 2-sided  $\alpha$  level of 0.05:

- Change from baseline (i.e., ratio) to Week 28 (Day 197) in CSF total SOD1 protein
- Change from baseline (i.e., ratio) to Week 28 (Day 197) in NfL in plasma
- Change from baseline to Week 28 (Day 197) in SVC
- Change from baseline to Week 28 (Day 197) in HHD megascore to assess muscle strength, as measured by the HHD device
- Time to death or permanent ventilation, which is defined as the time to the earliest occurrence of one of the following events:
  - Death
  - Permanent ventilation ( $\geq 22$  hours of mechanical ventilation [invasive or noninvasive] per day for  $\geq 21$  consecutive days)
- Time to death

The treatment effect will be assessed at each step at a 2-sided  $\alpha$  level of 0.05. The primary inference at each step will be based on the mITT population.

This procedure will control the Type I error for the secondary endpoints. If statistical significance is not achieved for a secondary endpoint, all secondary endpoints of a lower rank will not be considered statistically significant.

There will be no adjustment for multiple testing for the sensitivity or supplementary analyses for the primary and secondary endpoints, the exploratory endpoints or subgroup analyses.

The first and second endpoints in the ranking are PD endpoints, for which the analysis is described in Section 16.2.3.

The third secondary endpoint will be change from baseline to Day 197 in percent predicted SVC. If the number of deaths across both treatment arms is  $\geq 3$  (i.e.,  $\geq 5\%$  deaths out of a total of 60 patients in the mITT population), the primary inference will be based on the JRT methodology with MI to impute missing data; ANCOVA with MI for change from baseline will be used to obtain the estimates, and nominal p-values will be presented. If the number of deaths is  $< 3$  (i.e.,  $< 5\%$  deaths out of a total of 60 patients in the mITT population), ANCOVA with MI will be used as the primary analysis of this endpoint. The ANCOVA model will include treatment group as a fixed effect and covariates for baseline percent predicted SVC, baseline disease duration since symptom onset, and use of riluzole or edaravone. Treatment differences at other visits will also be derived from the model for exploratory purpose.

CONFIDENTIAL

The information contained herein may not be used, disclosed, or published without the written consent of Biogen MA Inc.

The secondary efficacy endpoints, time to death or permanent ventilation and time to death, will each be analyzed as time to event endpoints. Kaplan-Meier estimates of the cumulative probability of event occurrence over time will be determined. Treatment comparison will be based on a stratified log rank test. A Cox regression model will be used to obtain the hazard ratio and 95% confidence intervals for each of these endpoints. The analysis for each endpoint will also be repeated for the non-mITT population with nominal p-values presented.

[REDACTED]

### **16.2.3. Pharmacodynamics**

#### **16.2.3.1. Analysis Population**

The analysis of the PD and biomarker endpoints will be performed primarily for the mITT population but also for the non-mITT population.

#### **16.2.3.2. Methods of Analysis**

The PD endpoint, CSF total SOD1 protein at Day 197, will be the primary endpoint in the non-mITT population due to their likely slow clinical function decline. This is also the highest-ranked secondary endpoint in the sequential testing procedure for the mITT population, and NfL in plasma at Day 197 is the second highest ranked secondary endpoint. For other biomarkers, analyses will be performed for each of the mITT and non-mITT populations with nominal p-values presented. For each of the PD/biomarker endpoints, MI will be used to impute missing values. An ANCOVA model for log ratio to baseline will be performed on change from baseline values on the log scale for each of the imputed datasets for each PD/biomarker endpoint. The model will include covariates for the corresponding baseline value, i.e., log value, baseline disease duration since symptom onset, and use of riluzole or edaravone. Least square means (i.e., geometric mean ratios) for each treatment group with standard errors as well as treatment differences will be presented with 95% confidence intervals and p-values. The other exploratory PD/biomarker endpoints that will be analyzed in this way are NfL in CSF, and pNfH in CSF and plasma.

[REDACTED]. Treatment differences at other visits will also be presented with nominal p-values.

CONFIDENTIAL

The information contained herein may not be used, disclosed, or published without the written consent of Biogen MA Inc.

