#### **6.2.2.2. Pharmacodynamic Endpoint**

The secondary PD endpoint is the change from baseline in total SOD1 protein concentration in CSF.

CONFIDENTIAL

The information contained herein may not be used, disclosed, or published without the written consent of Biogen MA Inc.

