### **16.2.1. Clinical Function**

#### **16.2.1.1. Analysis Population**

The primary analyses of clinical function will be evaluated in the mITT population (see Section 8.2.1 for definition) comprising the subset of the population who meet prognostic enrichment criteria for rapid disease progression who are randomized and receive at least 1 dose of study treatment. The primary analysis population will comprise participants who meet prognostic enrichment criteria for rapid disease progression to enable detection of a statistically significant and clinically meaningful treatment effect on clinical function over the 6-month treatment duration. The treatment effect of clinical function endpoints in the non-mITT population will be analyzed, where relevant, with nominal p-values presented. The clinical function data in the overall ITT population will be summarized and analyzed where relevant.

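### Does calling CSF SOD1 the primary endpoint in the non-mITT population leave an uncontrolled second confirmatory test?

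*Protocol*

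**What the plan says.** Part C has one primary efficacy endpoint, the change in ALSFRS-R total score to Week 28. Its primary inference is in the mITT population, the participants who meet the enrichment criteria for rapid progression (Section 16.2.1.2.1). If it succeeds at two-sided 0.05, the secondary endpoints are tested in a fixed order, again in mITT, with CSF total SOD1 first (Section 16.2.1.2.2).

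For everyone else, the non-mITT population, the protocol says the following.

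- Section 16.2.1.2.2: "For the non-mITT and ITT populations, there will be no formal testing of efficacy endpoints. Testing of PD endpoints is discussed in Section 16.2.3".
- Section 16.2.3.2, to which that pointer leads: CSF SOD1 at Day 197 "will be the primary endpoint in the non-mITT population due to their likely slow clinical function decline". The next sentence gives the same measure the top secondary rank in mITT. Then: "For other biomarkers, analyses will be performed for each of the mITT and non-mITT populations with nominal p-values presented". Treatment differences at other visits are also called nominal. The Day 197 differences simply get p-values.
- Section 16.2.3.1: "The analysis of the PD and biomarker endpoints will be performed primarily for the mITT population but also for the non-mITT population".
- Section 6.2.2.2: "The secondary PD endpoint is the change from baseline in total SOD1 protein concentration in CSF".
- Section 16.2.7: 26 treated and 13 placebo participants give 97% power for a 25% reduction, with an SD of 0.216 on the natural log scale. No significance level is given in that paragraph.

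On multiplicity generally, Section 16.2.1.2.2 adds: "There will be no adjustment for multiple testing for the sensitivity or supplementary analyses for the primary and secondary endpoints". The same sentence extends this to exploratory endpoints and subgroup analyses.

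**The concern.** The word primary, joined to a power calculation, normally signals a confirmatory test. Here nothing states its significance level, its place in a sequence, or whether it is nominal. The bar on formal testing outside mITT covers efficacy endpoints only. PD testing is sent to Section 16.2.3, which attaches the word nominal to other biomarkers and other visits but not to this test.

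The omission stands out because the protocol is explicit elsewhere. For clinical function: "The treatment effect of clinical function endpoints in the non-mITT population will be analyzed, where relevant, with nominal p-values presented". For the time-to-event endpoints: "The analysis for each endpoint will also be repeated for the non-mITT population with nominal p-values presented". The label also seems at odds with the secondary status in Section 6.2.2.2 and with the priority given to mITT in Section 16.2.3.1.

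At stake is how a mixed result is reported. If ALSFRS-R misses in mITT, the sequence stops and SOD1 in mITT cannot be declared significant. The same measure in non-mITT might still be presented as a primary endpoint that was met.

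**Working it through.** **1. Does the stated power hold, and at what level?** Inputs from Section 16.2.7: n = 26 and 13, 25% reduction, SD 0.216 (log scale). Assumed: no change on placebo, two independent samples.

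- Effect: |ln(0.75)| = 0.2877.
- Standard error: 0.216 × √(1/26 + 1/13) = 0.216 × 0.3397 = 0.0734.
- Noncentrality: 0.2877 / 0.0734 = 3.92, with 26 + 13 − 2 = 37 degrees of freedom.

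| Two-sided level | Power, t | Power, normal |
|---|---|---|
| 0.025 | 93.9% | 95.3% |
| 0.05 | 96.8% | 97.5% |
| 0.10 | 98.6% | 98.9% |

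The plan's 97% is reproduced at 0.05, the level that the same section states for the mITT calculation. The missing level is thus recoverable, though only by inference.

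**2. Do the labels contradict each other?**

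| Section | What it ranks | Scope |
|---|---|---|
| 6.2.2.2 | SOD1 as secondary PD endpoint | Part C as a whole |
| 16.2.3.2 | SOD1 as main endpoint | non-mITT |
| 16.2.3.2, next sentence | SOD1 as top secondary endpoint | mITT |
| 16.2.3.1 | Order of analysis populations | PD and biomarker endpoints |

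All four can be true together. Section 16.2.3.2 gives SOD1 two roles, one for each population, in consecutive sentences. Section 16.2.3.1 ranks populations, not endpoints. The only mismatch is that Section 6.2 and the synopsis do not mention the non-mITT role.

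**3. What does the label mean in context?** Section 16.2.7 opens its non-mITT paragraph by saying that attention in that group will centre on the PD endpoint, because its clinical decline is expected to be slower. That explains the word. Section 16.2.4.2.1 calls the two groups subgroups by disease progression, so the sentence that waives adjustment for subgroup analyses can reasonably cover this test.

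**4. How large is the risk?** Two figures suggest themselves.

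- SOD1 significant in non-mITT while ALSFRS-R fails in mITT. The participants are disjoint, so (1 − 0.84) × 0.97 = 0.155, or 15.5%. This is computed under the plan's own assumption that SOD1 truly falls by 25%. These are correct detections, not errors.
- At least one false success over two independent tests at 0.05: 1 − 0.95² = 0.0975, or 9.75%. This needs both nulls to be true and the non-mITT test to be used as a second confirmatory primary. No section sets it up that way. Section 5.3.2 also reports a 37% reduction in CSF SOD1 at 100 mg, against none on placebo, in the earlier parts, so a null on SOD1 is not the likely case.

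**5. What would differ between the readings?** Formal or nominal, the analysis is the same ANCOVA on the log ratio to baseline with multiple imputation. It yields the same geometric mean ratio, 95% interval and p-value. ALSFRS-R and the mITT sequence keep their 5% level in both cases.

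**The case for a change.** The best case for a change is that the gap lies in the protocol's own scheme and is not merely detail held over for the SAP. The protocol sets out its multiplicity rules, defers this item by cross-reference, and the section it points to gives no answer. By naming other biomarkers and other visits as nominal, it invites a formal reading of what is left. Plasma NfL in non-mITT has the same unstated status, without the label. The rationale recorded for the amendment that enlarged Part C says the non-mITT group was increased to about 39 so that a statistically significant fall in SOD1 could be detected, which suggests that some claim was intended.

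The textual point stands: no sentence applies the word formal or nominal to this test. The consequence does not. The mITT error rate is unaffected and the output is identical.

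The amendment history also cuts against simply declaring the test nominal, since that gives up a claim the group was enlarged to support. The ambiguity could be closed equally well by a formal test with a stated level, or by one gated behind the mITT primary. At the stated 84% power for ALSFRS-R, the gated version has joint power of 0.84 × 0.968 = 81.3% to 0.84 × 0.975 = 81.9%. A split to 0.025 would keep about 94% to 95%. Choosing among these is a trade-off for the sponsor, not the correction of an error.

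**Conclusion.** No change to the plan is needed. The label is loose, and the status of one p-value is left for the reader to infer. Read in full, the protocol has a single confirmatory structure, in mITT at two-sided 0.05, and an SOD1 analysis that is the main interest in the remaining participants. There is no conflict with the secondary PD status. The power figure is right: 96.8% to 97.5% against the stated 97%, assuming two-sided 0.05 and no change on placebo. The primary inference and the mITT sequence carry no extra error.

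The 9.75% depends on a co-primary reading that the document does not state, and the 15.5% counts true effects found, so neither measures a defect. An analyst following the text would report the SOD1 ratio and interval in non-mITT. A careful report would not present the result as a confirmatory success if ALSFRS-R had failed. The p-value status of such a subgroup PD test is commonly settled in the SAP, which is not available here. This conclusion rests on reading non-mITT as a subgroup, which Section 16.2.4.2.1 supports but does not state for PD testing.
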